### 3.3 Apheresis Related Parameter Calculations

Parent container:

$$\text{Platelet Volume (mL)} = \frac{\text{Dual Bag Platelet Plus Product Weight (g)} - \text{Dual Bag Tare Weight(g)}}{1.02 \left(\frac{\text{g}}{\text{mL}}\right)}$$

$$\text{Plasma Volume (mL)} = \frac{\text{Plasma Bag Weight (g)} - \text{Plasma Bag Tare Weight(g)}}{1.03 \left(\frac{\text{g}}{\text{mL}}\right)}$$

$$\text{Average Platelet Concentration (x10}^3/\mu\text{L)} = \frac{1^{\text{st}} \text{ CBC (x10}^3/\mu\text{L)} + 2^{\text{nd}} \text{ CBC (x10}^3/\mu\text{L)}}{2}$$

$$\text{Platelet Yield (x10}^{11}\text{)} = \frac{[\text{Average Platelet Concentration}] * [\text{Dilution Factor}] * [\text{Platelet Volume}]}{100,000}$$

$$\text{Residual WBC Count (x10}^6\text{)} = \frac{[\text{Raw WBC Count (cells}/\mu\text{L)}] * [\text{Platelet Volume}]}{1,000}$$

Individual components (Products A, B, and C, where applicable, from the eCRFs):

$$\text{Platelet Volume (mL)} = \frac{\text{Bag Platelet Plus Product Weight (g)} - \text{Bag Tare Weight(g)}}{1.02 \left(\frac{\text{g}}{\text{mL}}\right)}$$

$$\text{Residual WBC Count (x10}^6\text{)} = \frac{[\text{Raw WBC Count (cells/}\mu\text{L)}] * [\text{Platelet Volume}]}{1,000}$$

### 3.4 Primary Endpoints

- Proportion of platelet units with an acceptable residual WBC level for single platelet products.
- Proportion of platelet units with an acceptable residual WBC level for double platelet products.
- Proportion of platelet units with an acceptable residual WBC level for triple platelet products.

The acceptable residual WBC level is defined as following:

For single platelet products: residual white blood cell measurement, rounded to the nearest tenth,  $< 5.0 \times 10^6$ .

For double platelet products:

- Parent container has a residual white blood cell measurement, rounded to the nearest tenth,  $< 8.0 \times 10^6$ ,
- If not met, each component residual white blood cell measurement, rounded to the nearest tenth,  $< 5.0 \times 10^6$ .

For triple platelet products:

- Parent container has a residual white blood cell measurement, rounded to the nearest tenth,  $< 12.0 \times 10^6$ ,
- If not met, each component residual white blood cell measurement, rounded to the nearest tenth,  $< 5.0 \times 10^6$ .

### 3.5 Secondary Endpoints

- Proportion of platelet units with an acceptable platelet yield for single platelet products.
- Proportion of platelet units with an acceptable platelet yield for double platelet products.
- Proportion of platelet units with an acceptable platelet yield for triple platelet products.

Acceptable platelet yield is defined as following, where the platelet yield is calculated from the formula in Section 3.3:

For single platelet products: platelet yield, rounded to the nearest tenth,  $\geq 3.0 \times 10^{11}$ .

For double platelet products: platelet yield, rounded to the nearest tenth,  $\geq 6.2 \times 10^{11}$ .

For triple platelet products: platelet yield, rounded to the nearest tenth,  $\geq 9.3 \times 10^{11}$ .

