Intended Use:	The Trima Accel system is an automated blood cell separator intended for use in collecting blood components for later transfusion into patients.
Study Centers Planned:	At least 2 and up to 8 Blood Centers in the United States
Objective:	To verify that platelets collected on the Trima Accel system with Version 7.0 software enhancements and stored in PAS meet the FDA requirements for leukoreduction ($< 5.0 \times 10^6$ residual white blood cells [WBC] per transfusable unit).
Rationale:	The study is designed to evaluate changes to the Trima Accel software to ensure the modified software meets the FDA acceptance criteria for leukoreduction and platelet yield. The operating range for the system flow rates, anticoagulant ratios, storage conditions, and centrifugal forces are the same as the currently cleared Trima Accel system. There are no changes to the environment or storage conditions for platelets; therefore, no in vitro or in vivo platelet quality data will be collected.
Outcome Measures:	
Primary Endpoint: The proportion of platelet units with an acceptable residual WBC level. Acceptable residual WBC counts are: singles = residual WBC level $< 5.0 \times 10^6$; doubles = residual WBC level $< 8.0 \times 10^6$ or $< 5.0 \times 10^6$ for each transfusable unit; and triples = residual WBC level $< 12.0 \times 10^6$ or $< 5.0 \times 10^6$ for each transfusable unit.
 
Secondary Endpoint: The proportion of platelet units with an acceptable platelet yield. Acceptable platelet yield for single, double and triple platelet products are: platelet yield $\geq 3.0 \times 10^{11}$ for singles, platelet yield $\geq 6.2 \times 10^{11}$ for doubles, and platelet yield $\geq 9.3 \times 10^{11}$ for triples.

Safety Measures:	Safety will be monitored through collection of adverse events (AEs), serious adverse events (SAEs), and unanticipated adverse device effects (UADEs).
Inclusion Criteria:	
 1. Age 18 years or older. 2. Meets the inclusion criteria defined by the Blood Center for an apheresis platelet with PAS collection on the Trima Accel system. These criteria are based on FDA guidance and American Association of Blood Banks (AABB) standards. Note: subjects who are deferred from volunteer community donations because of travel restrictions, piercings, or tattoos may participate in the study, as products are not transfused. 3. Has given written informed consent.

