6 RATIONALE FOR THE CURRENT STUDY

The study is designed to evaluate changes to the Trima Accel software (Version 7.0) to ensure they meet the FDA acceptance criteria for leukoreduction^{9,10} ($< 5.0 \times 10^6$ WBC per transfusable unit) and results in platelet yields $\geq 3.0 \times 10^{11}$ for singles, $\geq 6.2 \times 10^{11}$ for doubles and $\geq 9.3 \times 10^{11}$ for triples.

The operating range for the system flow rates, anti-coagulant ratios, storage conditions, and centrifugal forces are the same as the currently FDA cleared Trima Accel system. There are no

changes to the environment or storage conditions for platelets therefore no platelet quality data will be evaluated. Additionally, no products will be transfused from this study.

The Trima Accel system Version 7.0 software is intended to consolidate multiple enhanced software versions with the additional value of creating improvements relevant globally. This effort will yield a software release with several new enhancements targeted at improving productivity, leukoreduction and WBC flagging, reducing procedure time, reducing venous access alarms, and improving the user and donor experience.

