7.2 Secondary Endpoint

The proportion of platelet units with an acceptable platelet yield. Acceptable platelet yield for single, double and triple platelet products are presented in Table 7-2.

Table 7-2: Secondary Endpoint Acceptance Criteria

Parameter	Measured	Acceptance Criteria ^a
Platelet yield – Single Unit	Platelet concentration \times volume	Platelet yield is $\geq 3.0 \times 10^{11}$
Platelet yield – Double Unit	Platelet concentration \times volume	Platelet yield is $\geq 6.2 \times 10^{11}$
Platelet yield – Triple Unit	Platelet concentration \times volume	Platelet yield is $\geq 9.3 \times 10^{11}$

^a These yields represent typical lab minimums for splitting into double and triple platelet products.

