### 3.2 Study Populations

Analysis populations for this clinical investigation will be the Full Analysis Set (FAS) and Safety Populations.

For all analyses by platelet product, the platelet product type (single, double, triple, or unassigned) will be determined from the calculated platelet yield (see Section 3.3) using the following.

- If the platelet yield, rounded to the nearest tenth, is  $\geq 9.3 \times 10^{11}$ , then the product will be analyzed as a triple.
- Otherwise, if the platelet yield, rounded to the nearest tenth, is  $\geq 6.2 \times 10^{11}$ , then the product will be analyzed as a double.
- Otherwise, if the platelet yield, rounded to the nearest tenth, is  $< 6.2 \times 10^{11}$ , then the product will be analyzed as a single.
- Otherwise, if the procedure was not started, not completed or the platelet yield could not be determined for some other reason, as per the protocol analysis exclusion criteria, then the subject will be analyzed as “Unassigned”.

The Safety Population will include all subjects enrolled in this trial for whom at least 1 apheresis procedure is initiated. A procedure will be considered to have been initiated if a Trima procedure start date and time are present. The Safety Population will be used for all summaries except the primary and secondary endpoints and the derived apheresis related parameters.

Due to the design of the study, a given subject may be enrolled in the study on multiple occasions. These subjects may also qualify for the Safety Population more than once. If this occurs, the subjects will be analyzed separately for each enrollment.

The Full Analysis Set (FAS) will be defined separately for single, double, and triple platelet products and will not include any repeat subjects. The FAS for a given platelet product will consist of all collections that do not meet any of the exclusion criteria specified below. The FAS will be used to examine the primary and secondary endpoints and the derived apheresis related parameters.

Data points will be excluded from the FAS analysis in the following situations:

1. Inability to collect a complete unit due to:
  - a. Subject issues (inadequate access, reaction, needle abort, procedure disqualification upon Trima Accel device update of subject platelet count and hemoglobin or hematocrit).
  - b. Decision to stop procedure by subject, Investigator, nursing staff or operator.

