**Secondary Endpoint Acceptance Criteria**

Parameter	Measured	Acceptance Criteriaa
Platelet yield – Single Unit	Platelet concentration × volume	Platelet yield is $\geq 3.0 \times 10^{11}$
Platelet yield – Double Unit	Platelet concentration × volume	Platelet yield is $\geq 6.2 \times 10^{11}$
Platelet yield – Triple Unit	Platelet concentration × volume	Platelet yield is $\geq 9.3 \times 10^{11}$

a These yields represent typical lab minimums for splitting into double and triple platelet products.

Platelet yield will be summarized separately for single, double, and triple platelet products. The summaries will include N, mean, standard deviation, median, minimum, and maximum.

Separately for single, double, and triple platelet products, the lower one-sided 95% exact binomial confidence intervals (Clopper-Pearson) will be calculated for the proportion of platelet units with an acceptable platelet yield. If the lower one-sided confidence interval is greater than 75%, then it will be concluded that the proportion of platelet units with an acceptable platelet yield is at least 75% for the given platelet product.

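### Does rounding platelet yield to the nearest tenth in SAP 3.5 undercut the 3.0 × 10^11 limit for single products?

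*SAP*

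**What the plan says.** The protocol gives the single-product limit in the Synopsis ("platelet yield $\geq 3.0 \times 10^{11}$ for singles"), in Section 6 ("results in platelet yields $\geq 3.0 \times 10^{11}$ for singles") and in Table 7-2. None of these mentions rounding, and neither does the statistical plan in protocol Section 15. The acceptance table in SAP 3.7.3 repeats Table 7-2, also without a rounding rule.

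SAP 3.5, which defines the endpoint, does state one: "For single platelet products: platelet yield, rounded to the nearest tenth", followed by the comparison with 3.0 × 10^11. The same convention appears in two other places:

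- SAP 3.2, for assigning product type ("Otherwise, if the platelet yield, rounded to the nearest tenth, is" below 6.2 × 10^11, the product is analysed as a single).
- SAP 3.4, for the primary endpoint ("For single platelet products: residual white blood cell measurement, rounded to the nearest tenth", which must be below 5.0 × 10^6).

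The decision rule in SAP 3.7.3 uses a one-sided 95% Clopper-Pearson lower limit: "If the lower one-sided confidence interval is greater than 75%, then it will be concluded" that at least 75% of units have an acceptable yield.

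**The concern.** Read literally, the plan holds two versions of one criterion. A single product at 2.97 × 10^11 passes under SAP 3.5 and fails under protocol Table 7-2 and the table in SAP 3.7.3. For yield, rounding to the nearest tenth moves the working limit in the lenient direction.

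The pass rule is also tight. At 93 products, 16 failures pass and 17 fail, so one borderline product could decide the result. The report could then state that at least 75% of singles reach 3.0 × 10^11 when the data support that only for 2.95 × 10^11.

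**Working it through.** **Inputs.** 93 products per type and at most 16 yield failures (protocol 15.1, SAP 3.1); one-sided 95% Clopper-Pearson lower limit, to exceed 75% (SAP 3.7.3); limits of 3.0, 6.2 and 9.3 × 10^11 (SAP 3.5). The documents give no mean or SD for yield, so any distribution below is an assumption.

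**1. The plan's own rule.** With f failures in n, the lower limit is the 5th percentile of Beta(n − f, f + 1).

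- n = 93, f = 16 (77/93 acceptable): 75.05%, pass.
- n = 93, f = 17 (76/93 acceptable): 73.85%, fail.
- P(at most 16 failures of 93) when the true acceptable share is exactly 75%: 0.0489.

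The stated rule reproduces. Rounding changes which singles count as failures, not the rule.

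**2. The working limit.** 2.949 rounds to 2.9 (fails) and 2.95 rounds to 3.0 (passes), whether halves are rounded up or to even. The gap is 3.00 − 2.95 = 0.05, and 0.05/3.00 = 1.7% of the limit.

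**3. Which products can be affected.** SAP 3.2 assigns doubles and triples by rounded yield at 6.2 and 9.3, the same cut-offs SAP 3.5 tests. Their yield result cannot change through the rounding in 3.5, so only singles remain.

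**4. Direction on the primary endpoint.** A residual WBC count of 4.95 × 10^6 rounds to 5.0 and fails the requirement to be below 5.0. The convention is strict there and lenient for yield.

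**5. Size at the 75% boundary.** Let q be the share of singles in [2.95, 3.00) × 10^11, with exactly 75% truly at or above 3.00. The chance of passing is P(X ≤ 16), X ~ Binomial(93, 0.25 − q):

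| q | chance of passing |
|---|---|
| 0 | 4.9% |
| 0.5% | 6.1% |
| 1% | 7.5% |
| 2% | 11.2% |

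These are false passes only if unrounded 3.00 is taken as the criterion. Under the definition in SAP 3.5 the error at its own 75% boundary stays at 4.9%.

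**6. Size away from the boundary.** If 90% of singles truly reach 3.00 and q = 1%, the chance of passing is 0.990 unrounded and 0.996 rounded. Under assumed normal yields (× 10^11):

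| mean, SD | share ≥ 3.00 | share ≥ 2.95 | singles of 93 in the band | chance of passing, unrounded → rounded |
|---|---|---|---|---|
| 3.2, 0.3 | 0.748 | 0.798 | 4.67 | 0.04 → 0.28 |
| 3.4, 0.4 | 0.841 | 0.870 | 2.64 | 0.70 → 0.91 |
| 3.6, 0.4 | 0.933 | 0.948 | 1.37 | 1.00 → 1.00 |
| 4.0, 0.4 | 0.994 | 0.996 | 0.17 | 1.00 → 1.00 |

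The effect is visible when typical yields sit just above the limit and disappears when they do not.

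**7. Cost of moving to unrounded yield throughout.** If product type in SAP 3.2 were also assigned on unrounded yield, products just under 6.2 or 9.3 × 10^11 would drop a class and meet a different WBC limit. A class could then fall to 92. With one WBC failure the lower limit is 94.95% at 92, against 95.0006% at 93, so a primary result could be lost over a secondary-endpoint convention.

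**The case for a change.** The strongest case for a change is that fixing the rounding in SAP 3.5 does not remove the conflict with Table 7-2 and the SAP's own acceptance table. A reader of the report would see 3.0 × 10^11 in the table and would not know that 2.95 counts. Singles are the only class in which the yield test can fail, so the rounding loosens the limit exactly where it matters. The rows for means of 3.2 and 3.4 show that the chance of passing can move appreciably.

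Part of this stands. The tables and the definition are worded differently, and the rounding is lenient for singles. Three things limit it:

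- The section that defines the endpoint is explicit, so an analyst has one rule to apply. The table in SAP 3.7.3 is a reprint of the protocol's summary.
- A limit printed as 3.0 can reasonably be read as applying to a value reported to one decimal. The protocol neither requires nor forbids that, and supplying such detail is the SAP's job.
- The larger shifts need yields concentrated just above 3.0, which nothing in the documents supports or excludes. Since SAP 3.2 also counts every completed product below 6.2 × 10^11 as a single, including doubles that fell short, a very tight distribution near 3.0 is doubtful.

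That one product can turn a pass into a fail is true of any cut-off and says nothing about rounding.

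**Conclusion.** The concern does not call for a change. The arithmetic behind it is right: singles from 2.95 × 10^11 pass, a margin of 1.7%. But this is a convention fixed in advance, set to the precision of the printed limits and applied alike to product type, WBC and yield. Keeping rounding where it is strict and dropping it where it is lenient would put two conventions in one plan, and carrying unrounded yield into product assignment would put primary-endpoint class sizes at risk.

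What remains is a difference in wording between a definition and its summary tables. SAP 3.5 settles how the analysis is run. SAP 1.0 and 3.7 promise listings of all variables and all eCRF data, and SAP 3.3 gives the yield formula, so anyone who prefers the literal limit can recount singles at unrounded 3.00 × 10^11.

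This rests on reading SAP 3.5 as the operative definition. The practical effect cannot be stated more closely than the ranges above without yield data; if no single falls in the band, it is nil.

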### 3.6 Safety Endpoints

Safety will be monitored through collection of adverse events (AEs), serious adverse events (SAEs), unanticipated adverse device effects (UADEs), and device deficiencies.

### 3.7 Statistical Analysis

All data collected on the eCRFs will be presented in the listings. Missing data will not be imputed. All analyses will be based on observed data only.

#### 3.7.1 Demographic and Baseline Characteristics

Demographic and baseline characteristics will be summarized by platelet products (single, double, triple, and unassigned) and overall. Categorical variables (such as gender and race) will be summarized by frequency and percentage. Continuous variables (such as weight and height) will be summarized by N (number of non-missing observations), mean, standard deviation, median, minimum, and maximum.

#### 3.7.2 Disposition

Study completion status and reasons for discontinuation will be displayed by platelet products (single, double, triple, and unassigned) and overall using frequencies and percentages.

#### 3.7.3 Efficiency Analysis

##### Primary Endpoints

##### Primary Endpoint Acceptance Criteria

Parameter	Measured	Acceptance Criteria
Residual WBC Count – Single Unit	Flow cytometry; BD Leukocount™ or equivalent	Residual WBC count is $< 5.0 \times 10^6$
Residual WBC Count – Double Unit	Flow cytometry; BD Leukocount or equivalent	Residual WBC count is $< 8.0 \times 10^6$ or each component $< 5.0 \times 10^6$
Residual WBC Count – Triple Unit	Flow cytometry; BD Leukocount or equivalent	Residual WBC count is $< 12.0 \times 10^6$ or each component $< 5.0 \times 10^6$

Abbreviations: WBC = white blood cell.

Summary statistics will be provided separately for single, double, and triple residual WBC levels. The summaries will include N, mean, standard deviation, median, minimum, and maximum.

Frequencies and percentages of platelet units with an acceptable residual WBC level and the lower one-sided 95% exact binomial confidence intervals (Clopper-Pearson) will be calculated separately for single, double, and triple platelet products. If the lower one-

sided confidence interval is greater than 95%, then it will be concluded that the proportion of platelet units with an acceptable residual WBC level is at least 95% for the given platelet product.

Secondary Endpoints

**Secondary Endpoint Acceptance Criteria**

Parameter	Measured	Acceptance Criteriaa
Platelet yield – Single Unit	Platelet concentration × volume	Platelet yield is $\geq 3.0 \times 10^{11}$
Platelet yield – Double Unit	Platelet concentration × volume	Platelet yield is $\geq 6.2 \times 10^{11}$
Platelet yield – Triple Unit	Platelet concentration × volume	Platelet yield is $\geq 9.3 \times 10^{11}$

a These yields represent typical lab minimums for splitting into double and triple platelet products.

Platelet yield will be summarized separately for single, double, and triple platelet products. The summaries will include N, mean, standard deviation, median, minimum, and maximum.

Separately for single, double, and triple platelet products, the lower one-sided 95% exact binomial confidence intervals (Clopper-Pearson) will be calculated for the proportion of platelet units with an acceptable platelet yield. If the lower one-sided confidence interval is greater than 75%, then it will be concluded that the proportion of platelet units with an acceptable platelet yield is at least 75% for the given platelet product.

**3.7.4 Calculated Apheresis Related Parameters**

The average platelet concentration, platelet yield, and residual WBC count as specified in Section 3.3 will be summarized by N, mean, standard deviation, median, minimum, and maximum for each platelet product type.

**3.7.5 Safety Analysis**

All adverse events will be coded using MedDRA and reported by SOC and preferred term. The focus of the adverse event summaries will be on treatment-emergent adverse events. Adverse events will be considered treatment-emergent if they occur on or after the start of the apheresis procedure, as defined in Section 3.2. Adverse events (AEs), serious adverse events (SAEs), and unanticipated adverse device effects (UADEs) will be summarized with frequencies and percentages. Additional summaries of AEs will be presented for the maximum reported severity and relationship to device and procedure. AEs leading to study or procedure discontinuation will also be tabulated. Summaries will be presented by platelet products (single, double, triple, and unassigned) and overall.

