10.2.2 Apheresis Procedure

Plateletpheresis will be per site standard practice and per applicable FDA guidelines such as the “Guidance for Industry and FDA Review Staff: Collection of Platelets by Automated Methods, December 2007” and the “Guidance for Industry: Pre-Storage Leukocyte Reduction of Whole Blood and Blood Components Intended for Transfusion, September 2012”.^{9,10}

Apheresis procedures will be run according to the instructions and precautions described in the Version 6.0 Trima Accel Operator’s Manual and the Version 7.0 user change summary.

The following procedures will be performed:

1. Venipuncture.
2. Collect venous whole blood sample.
 - a. Complete blood count (hemoglobin or hematocrit and platelet count).
3. Update Trima Accel device with updated platelet count and hemoglobin or hematocrit.

4. Perform apheresis procedure.
5. Record the following:
 - a. Type of cuff used.
 - b. Trima procedure details.
 - c. AEs, SAEs and UADEs.
 - d. Medical interventions to treat AEs, if applicable.
 - e. Device deficiencies.

This will conclude the subject's participation.

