13.1.2 Venipuncture Related

The risks associated with venipuncture for blood sampling or intravenous (IV) access include apprehension, pain, discomfort, venospasm, fainting, bruising, infiltration at the venipuncture site, clotting in the IV tubing, and/or administrative errors. Occurrence rates of venipuncture AEs are summarized in Table 13-1.

Table 13-1: Venipuncture Adverse Event Frequency

Location	Very Common ≥ 1/10	Common ≥ 1/100 to < 1/10	Uncommon ≥ 1/1,000 to < 1/100	Rare ≥ 1/10,000 to < 1/1,000	Very rare < 1/10,000	Not known Sporadic case reports
General ^{11,13-15}	Apprehension	Presyncope ^a	Faint ^b			
At puncture site ^{11,13,14,17}		Hematoma		Nerve irritation	Arterial puncture	
		Pain		Infection		
Distant of puncture site ^{11,13,14,16}		Discomfort			Skin allergy	Phlebitis
					Neuropathic pain	DVT

Abbreviations: DVT = deep venous thrombosis

^a Presyncope includes symptoms such as pallor, lightheadedness, dizziness, nausea, diaphoresis.

^b Faint defined as a brief loss of consciousness, usually less than 30 seconds.

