13.7.2 SAE/UADE Reporting

Any AE/SAE/UADE that occurs after signing the ICF until study completion/termination must be reported. Follow-up (regardless of relationship to the study treatment/procedure[s]) must be reported and an AE/SAE/UADE Form must be submitted to Terumo BCT within 24 hours of knowledge of the event to:

Terumo BCT
Email: [contact]
[contact]

Terumo may request additional information from the Investigator to ensure the timely completion of accurate safety reports.

Additionally the SAE/UADE must be entered on the AE page(s) of the CRF. Follow-up SAE/UADE reports need to be submitted to Terumo BCT as soon as additional information regarding the event becomes available.

Terumo BCT will be responsible for reporting SAE/UADEs to the regulatory authorities in accordance with applicable regulatory reporting guidelines. The Investigator is responsible for submitting SAE/UADEs to his/her Institutional Review Board (IRB) as required by local policy.

Exclusions to SAE/UADE Reporting Requirements

The following are not considered SAEs/UADEs:

- Planned hospitalization.
- Anticipated day-to-day fluctuations of pre-existing condition(s) present or detected at the start of the study that do not worsen.

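### The SAP ties both its treatment-emergent window and its Safety Population to the Trima start stamp, which may leave needle-placement events and needle-stuck donors without a stamp out of the main AE tables that the protocol plans for all AEs

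*SAP*

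**What the plan says.** **Window.** SAP 3.7.5 gives the rule as "Adverse events will be considered treatment-emergent if they occur on or after the start of the apheresis procedure" and refers to SAP 3.2 for the definition. The section it points to says: "A procedure will be considered to have been initiated if a Trima procedure start date and time are present".

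**Scope of the tables.** SAP 3.7.5 opens with "All adverse events will be coded using MedDRA and reported by SOC and preferred term" and continues with "The focus of the adverse event summaries will be on treatment-emergent adverse events". Protocol 15.2.3 plans frequency tables of all AEs, SAEs and UADEs in the safety population, with no treatment-emergent filter. Protocol 13.4 records AEs from signing of the consent form.

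**Order on Day 1.** Protocol 10.2.2 numbers the steps: venipuncture first, then "Collect venous whole blood sample", then the device update, and performing apheresis fourth.

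**Population.** Protocol 15.3 and SAP 3.2 both require an initiated apheresis procedure for the Safety Population. Only the SAP says what initiated means, namely that the stamp is present. The SAP uses this population for every summary except the endpoints and the derived apheresis parameters. SAP 3.2 also creates an Unassigned group that includes procedures never started, and SAP 3.7.5 presents safety by that group.

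**End of reporting.** Protocol 10.2.2 ends participation with the apheresis visit. Protocol 13.7.2 says: "Any AE/SAE/UADE that occurs after signing the ICF until study completion/termination must be reported".

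**The concern.** Venipuncture is the part of the visit with its own risk table. Protocol 13.1.2 says "Occurrence rates of venipuncture AEs are summarized in Table 13-1", and that table rates presyncope, hematoma, pain and discomfort as common. Protocol 13.1.1 adds that almost 40% of the (rare) reactions needing outside medical care are venipuncture related. At half the sites the sponsor's arm cuff is in use, and protocol 2.2 describes it as fully inflated for obtaining venipuncture.

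A window that opens after needle placement would miss early events at that step. A population defined by the same stamp would also miss the donors for whom needle placement went badly enough that the procedure never began. Both errors push the reported donor AE counts downward. In addition, the two documents describe different tables, so two programmers could produce different results from the same data.

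**Working it through.** The plan states no figure for the AE window, so there is none to reproduce. The check sets the texts side by side, then sizes what could be affected.

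**1. Which AEs are tabulated?** Protocol 15.2.3: all AEs in the safety population. SAP 3.7.5: all AEs coded and reported, with the summaries focused on treatment-emergent ones. The SAP does not say whether its severity, relationship and discontinuation tables use all AEs or only the treatment-emergent subset. The two documents are therefore not aligned.

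**2. Where does the window open relative to the needle?** By protocol 10.2.2, performing apheresis is step 4 and the needle is step 1. If the stamp belongs to step 4, an AE with onset during steps 1 to 3 is not treatment-emergent. No text says which action creates the stamp, so its position is an inference. An AE from the screening venipuncture (protocol 10.1, up to 30 days earlier, in some subjects) is not treatment-emergent wherever the Day 1 stamp falls, unless its onset is delayed until after the stamp.

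**3. Which donors drop out?** The protocol foresees ways to stop early:
- inadequate access, needle abort, or disqualification at the device update (15.4, item 1a);
- a venous platelet count that qualifies the donor for a product type already full (10.3, item 3).

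Any such donor without a stamp is outside the Safety Population and so outside the safety tables. The Unassigned column of those tables can then hold procedures started but not completed. It cannot hold the never-started ones that SAP 3.2 assigns to that group.

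**4. How many events?** Inputs: the common band of Table 13-1, 1/100 to below 1/10; a lower count of 3 × 93 = 279 evaluable procedures; an upper count of 450, the enrolment cap. The cap includes screen failures, so it overstates the number exposed. Expected events per common item = n × p:

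| n | p = 0.01 | p = 0.10 |
|---|---|---|
| 279 | 2.79 | 27.9 |
| 450 | 4.5 | 45 |

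Events before the stamp = s × n × p, where s is the share with onset between needle and stamp. The documents give no value for s. With s from 0 to 1, the result runs from 0 to just under 45 per item. This bounds the pool of events and does not estimate the loss. The number of donors with a needle stick and no stamp cannot be derived either.

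**5. Where does the window close?** The SAP rule has no end. Protocol 10.2.2 schedules no contact after the visit, and 13.7.2 does not say whether completion means the subject's or the study's. For an item rated rare (1/10,000 to below 1/1,000), expected events run from 279 × 0.0001 = 0.028 to 450 × 0.001 = 0.45. Late-onset items with a stated frequency, such as infection (rare) and neuropathic pain (very rare), would therefore hardly be seen in this trial even with active follow-up.

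**The case against.** The strongest case on the other side has four parts.

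- **Nothing is removed from reporting.** The SAP says all AEs are reported by SOC and preferred term, calls treatment-emergent events only the focus, and in 3.7 lists all eCRF data. This stands. A reader might infer that venipuncture harms fall outside the safety tables as a class, and the documents do not support that. The rule also depends on onset, not cause: a hematoma or nerve irritation from the needle that begins after the stamp is counted.
- **The late stamp is not documented.** Venipuncture is itself listed under the protocol heading for the apheresis procedure. Protocol 15.4 says the actual platelet count comes from the sample pouch of the Trima disposable, so the set is already in use before the device update. The stamp might therefore precede step 4. This stands as a limit on the claim. It is also a reason not to rest the window on an undefined trigger.
- **Delayed harms are a separate matter.** A reader might infer that the SAP excludes them, or that a donor hospitalised the next day need not be reported. The SAP window never closes, protocol 13.7.1 requires any SAE or UADE to be reported within 24 hours of knowledge, and 13.7.2 is ambiguous about whose completion ends reporting. What remains is that no later contact is scheduled and the end point needs stating.
- **The consequence is modest.** Safety is descriptive here, with no hypothesis or decision rule, and the objective is leukoreduction. This is true, and it limits the weight of the point. It does not settle the mismatch with protocol 15.2.3 or the donors lost from the denominator.

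**Conclusion.** The point holds in a limited form. The SAP's treatment-emergent focus is narrower than the tables the protocol plans, and the Safety Population depends on the same stamp. If the stamp follows needle placement, AEs beginning in between are missing from the treatment-emergent summaries but present in the listings. Donors with a needle stick and no stamp are missing from the safety tables altogether, although the Unassigned group was written to include procedures not started.

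This rests on one inference, the timing of the stamp, drawn from the step order in protocol 10.2.2. The size is unknown: the direction is toward undercounting, but no particular number of lost events can be defended from the documents. The delayed-harm part is mainly a matter of stating when reporting ends and labelling the tables to match.

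**What to change.** 1. **SAP 3.7.5:** define treatment-emergent as onset at or after Day 1 venipuncture. The recording list in protocol 10.2.2 names no needle time, so if none is captured, use the Day 1 date and the order of steps. Alternatively, tabulate all AEs after consent, as protocol 15.2.3 states; this would also cover the screening venipuncture. Either way, say for each table which set of AEs it uses.
2. **SAP 3.2:** include subjects with Day 1 venipuncture but no Trima start stamp in the Safety Population, or tabulate them separately. Changing the window alone would not bring these donors in. Protocol 15.3 does not define initiation, so the SAP's operational rule can be reworded; a separate table leaves the existing population untouched.
3. **Protocol 10.2.2 and 13.7.2:** reconcile the two on when AE reporting ends, and label the AE tables with the period they cover.

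The cost is wording and a little programming, with no added visit, because AEs are already recorded from consent. Reported AE counts may rise slightly and the safety denominator may be slightly larger.
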